4. STUDY POPULATION

4.1 Patient selection (Study population)

Patients enrolled in this study will have at least one of the indications listed below and meet all of the inclusion criteria. Patients meeting any of the exclusion criteria are not eligible for this study. The surgeon together with the patient will decide if uncemented THA is appropriate. The study will be performed in Noordwest Ziekenhuisgroep Alkmaar, in which in 2013 665 hip replacements were performed, of which about 80% were uncemented total hip replacements.

4.2 Subject inclusion

Subjects must meet all of the following characteristics for inclusion in the study.

- Willing and able to participate in the study protocol.
- Patient requires Primary total hip replacement (THR) to the affected side, unilateral or bilateral.
- Patient agreed to participate in the study by signing the Informed Consent form.
- Age of patient at date of surgery 18 to 75 years.
- Patient is likely to comply with study follow-up requirements
- ASA Physical Status I & II
- Diagnosed with osteoarthritis of the hip
- Subjects for who it is decided that they will undergo an uncemented THA at Noordwest Ziekenhuisgroep Alkmaar.
- Subjects who are able to give voluntarily, written informed consent to participate in this clinical investigation and from whom consent has been obtained.
- Subjects, who, in the opinion of the Clinical Investigator, are able to understand this clinical investigation, cooperate with the investigational procedures and are willing to return for all the required post-treatment follow-ups.

4.3 Subject exclusion

Subjects with any of the following characteristics must be excluded from the participation in the study.

- Previous surgery to ipsilateral or contralateral hip.
- Patients with posttraumatic changes of the pelvis or femur;

- Patients with inflammatory arthropathies;
- Patients diagnosed with rheumatoid arthritis
- Patients who suffer from insulin dependent diabetes
- Patients who are treated for or diagnosed with neurological or muscle disorders which make assessment of pain and gait not possible
- Patients who use medication for osteoporosis
- Pronounced coxa valga with a femoral neck angle $> 145^{\circ}$
- Pronounced coxa vara with a femoral neck angle $< 125^{\circ}$
- History of infection in the affected joint; systemic infections
- Patients who lack understanding of the Dutch language
- Patients who are treated for or diagnosed with neurological or muscle disorders which make assessment of pain and gait not possible
- Grossly insufficient femoral or acetabular bone stock in the involved hip where a revision cup is indicated
- Spinal disease with neurologic movement disorders
- Alcoholism or addictive disorders
- Body mass index (BMI) > 30
- Patient is pregnant or being pregnant during follow up intervals
- Patients who lack understanding of the Dutch language

4.4 Sample size calculation

The main hypothesis of this study is that the NANOS short stem prosthesis will show less subsidence if placed by means of the DAA compared to the PLA at two years follow-up. No previous studies have been published in which differences in subsidence between DAA and PLA are compared for short stem prostheses.

The study design of the present study is an RCT. We calculated our sample size based on the study of Budde et al.¹⁵. In this study a mean subsidence of 0.46 ± 0.31 mm was measured for the NANOS stem prosthesis after 2 years of follow-up. When assuming a mean subsidence of 0.46 mm in the PLA group and 0.25 mm less subsidence in the DAA group, a sample size of 25 subjects in each group (a total of 50 subjects) is necessary to detect a difference with a power of 80% and a two-sided 5% significance level using an independent t-test.

Since the follow-up of patients is almost similar to the regular follow-up of patients that undergo total hip replacement, we do not expect a high number of patients that are lost to follow-up. Therefore, we will include 10% more patients, which resulted in 56 patients.

5. TREATMENT OF SUBJECTS

Two surgeons will be placing the NANOS stems. Both surgeons will use the direct anterior approach (DAA) and the posterolateral approach (PLA). Both surgeons have extensive experience with both these approaches and previous experience with the NANOS stem.

We will use a follow-up protocol that is similar to the NOV (Dutch orthopedic society) THA guidelines¹⁶. This protocol contains postoperative clinical and radiological visits at 8 weeks and one year. In addition, we will send patients functional evaluation questionnaire (HOOS, VAS) at 3 and 6 months. At 24 months we will schedule an additional clinical and radiological follow-up visit.

5.1 Investigational product/treatment

The NANOS short stem femoral component (Smith & Nephew, Memphis, Tennessee, United States of America) in combination with the R3 acetabular component (Smith & Nephew, Memphis, Tennessee, United States of America) will be placed. Both components are ODEP rated. The NANOS stem has previously been placed in the hospital in a research setting investigating short to medium survivorship and function and showed excellent results.

All patients will be submitted to standard postoperative physical therapy and analgesia protocols.

The prosthesis will be placed using a direct anterior or posterolateral approach. Both approaches are regularly performed in hospitals and clinics in the Netherlands and in Noordwest Ziekenhuisgroep location Alkmaar specifically. The two surgeons involved in the study have extensive experience with both approaches and perform at least 40 total hip replacements each year. Therefore, no specific surgical learning curve is expected for either of the procedures.

For the DAA, the patient is placed in a supine position. The hip capsule is reached from the front, utilizing the internervous plane, located between the sartorius muscle and tensor fascia latae muscle superficially, and between the rectus femoris muscle and gluteus medius muscle more profoundly.

The PLA is the most commonly used approach overall in the Netherlands. For the PLA, the patient is placed in the lateral position. The hip capsule is reached from the back, after incising the tensor fascia lata muscle and gluteal fascia, blunt dissection of the gluteus

maximus muscle, and releasing the insertions of the piriformis, gemelli and obturator externus tendons.

Intra- and postoperatively patients will be treated according to the standard clinical hip replacement protocol implemented in the NWZ. For a detailed description of the standard postoperative pain protocol see appendix.

Nanos

Manufacturer: Smith & Nephew
Product Type: Hip Stems
Fixation: Cementless
Modularity: Monobloc
Date of first use: 2004

[more information >](#)

R3 Tri-bearing acetabular cup

Manufacturer: Smith & Nephew
Product Type: Hip Cups
Fixation: Cementless
Modularity: Modular
Date of first use: 2007

[more information >](#)

5.2 Use of co-intervention (if applicable)

Not applicable

5.3 Escape medication (if applicable)

Not applicable

6. DESCRIPTION OF THE DEVICES

6.1 Implants

In this study, the NANOS neck preserving stem will be used in combination with a well-documented non-cemented acetabular cup the R3 (R3 smith & nephew, Memphis, Tennessee, United States of America) which is on the NOV list of approved components.

Nanos

Manufacturer: Smith & Nephew
Product Type: Hip Stems
Fixation: Cementless
Modularity: Monobloc
Date of first use: 2004

[more information >](#)

R3 Tri-bearing acetabular cup

Manufacturer: Smith & Nephew
Product Type: Hip Cups
Fixation: Cementless
Modularity: Modular
Date of first use: 2007

[more information >](#)

6.2 articulation

Acetabular component will be the R3 (Smith & Nephew, Memphis, Tennessee, United States of America). All investigators will use a oxinium head and a highly crosslinked polyethylene insert (XLPE) insert. Head size will be 32 mm or 36 mm. The size of the head depends on the acetabular component. Smaller heads will only be used if the acetabulum requires a cup size in which 32 mm cannot be used.

6.3 instruments

The participating surgeons will only use instrument supplied by Smith & Nephew orthopaedics AG for the implantation of the NANOS neck preserving stem. All instruments will be used conform the instruction of the manufacturer.

6.4 Applicable norms and guidelines

Clinical Investigation: ISO 14155:1 and ISO 14155:2

Reporting: STROBE: Strengthening the Reporting of Observational Studies in Epidemiology).

7. NON-INVESTIGATIONAL IMPLANT

7.1 Name and description of non-investigational product(s)

Not applicable

7.2 Summary of findings from non-clinical studies

Not applicable

7.3 Summary of findings from clinical studies

Not applicable

7.4 Summary of known and potential risks and benefits

Not applicable

7.5 Description and justification of route of administration and dosage

Not applicable

7.6 Dosages, dosage modifications and method of administration

Not applicable

7.7 Preparation and labelling of Non Investigational Medicinal Product

Not applicable

7.8 Drug accountability

Not applicable

8. METHODS

8.1 Study parameters/endpoints

8.1.1 Main study parameter/endpoint

- Radiographic analysis will be done on standard AP and lateral view X-rays postoperative, 8 weeks, 12 months and 24 months. Only the two X-rays that are taken during the extra outpatient appointment at 24 months do not include the standard treatment for THR. To measure migration and stem positioning we will use the EBRA-FCA software system. A blinded practitioner of the department of radiology will mark nineteen reference points on the stem and femur. The software automatically defines all other parameters.

8.1.2 Secondary study parameters/endpoints

Secondary study parameters are the clinical, functional and surgical outcome parameters compared between the DAA and PLA:

- Perceived pain, measured using a Visual Analogue Scale (VAS) in the week before surgery, during hospitalization at days 1 to 3, at discharge, 8 weeks, three months, six months, one year after surgery and two years after surgery.
- Hip pain and symptoms assessed using the symptoms, pain and activities of daily living (ADL) subscales of the Hip Dysfunction and Osteoarthritis Outcome Score (HOOS) in the week before surgery, at 8 weeks, three months, six months, one year after surgery and two years after surgery.
- Hip range of motion in the week before surgery, at 8 weeks, three months, six months, one year after surgery and two years after surgery.
- Quality of life assessed using the EQ-5D in the week before surgery, at 8 weeks, three months, six months, one year after surgery and two years after surgery.
- Functioning during daily living assessed using the HOOS in the week before surgery, at 8 weeks, three months, six months, one year after surgery and two years after surgery.
- Hip abductor strength and gait quality before surgery, at 8 weeks and after 12 months.
- Length of hospital stay
- Operation time, blood loss, and other parameters of the surgical procedures
- All complications related to the surgery and rehabilitation
- Health status will be classified using the ASA score.
- Patient's pre-operative status, surgical procedure as well as clinical and radiological outcome will be documented.

8.1.3 Other study parameters

Patient characteristics such as age, gender, stature, body weight, body length, side of operation (left or right), smoking and comorbidities.

8.2 Randomization, blinding and treatment allocation

When patients want to participate, informed consent will be signed. Baseline measurements will be registered and patients will be randomized to one of the two study arms. Patient or surgeon will not be blinded for type of treatment.

8.3 Study procedures

Pre-operative assessment

After inclusion participants will be asked to fill in the questionnaires. A general questionnaire containing questions about demographic characteristics of the participants, and validated questionnaires to assess clinical and functional outcomes will be used. The Hip Dysfunction and Osteoarthritis Outcome Score (HOOS)¹⁷ will be used to assess pain, symptoms and function of the hip in relation to different activities of daily life. Also, a Visual Analogue Scale (VAS) will be used to assess perceived pain in the previous week. To assess quality of life, the participant will be asked to fill in the EQ-5D^{18,19}.

In addition to the self-reported HOOS, the quality of movement and walking will be quantified to assess functional outcome. Basic balance and gait performance will be tested using the timed “up & go” (TUG) test, instrumented with inertial sensors to measure body segment accelerations and angles, and a two times 50 meter walk at their preferred walking speed, also instrumented with inertial sensors⁸⁻¹². For the TUG test¹³, in short, participants will be asked to stand up from a chair, walk for 3 meters, walk back to the chair and sit down on the chair. The time needed to perform the TUG as instructed will be registered. In addition, the participants will wear inertial sensors (McRoberts Dynaport Hybrid, Dimensions 87 x 45 x 14 mm, Weight 74 grams)¹⁴, which will be attached to the lower back with Velcro fixation. The inertial sensors measure the accelerations and angles of the lower leg as well as stance and tilt of the pelvis. Pre-operatively, standardized calibrated radiographs of the pelvis (anterior posterior or AP and lateral views) are performed.

Measurement of subsidence:

The EBRA-FCA system measures subsidence offset and varus/valgus angulation using at least four standardized AP standing pelvic x-rays. It can detect axial subsidence of 1 mm with a specificity of 100% and sensitivity of 78%. This system has been validated for short stem hip implants and has been previously used for the NANOS stem. Progressive subsidence of >1.5 mm two years after prosthesis placement is an indicator for aseptic loosening^{5,7,20}. Subsidence will be measured by independent and blinded radiologists.

Assessments during surgery and hospital stay

Operation parameters such as operation time and blood loss will be registered. During the first 3 days after surgery, on the second postoperative day standing AP radiographs of the pelvis will be made. The two orthopedic surgeons involved in the study have experience with placement of the NANOS stem. Each surgeon performs about 40 to 100 total hip replacements each year. Both surgeons are experienced in performing either the direct anterior approach or the posterolateral approach. The total time of hospital stay will be registered. Complications and adverse events are noted at discharge.

Follow-up assessments

A questionnaire including the HOOS, VAS, EQ-5D and complications has to be completed by the participant at the regular follow-up visits at the orthopaedic outpatient department at 8 weeks (± 14 days) and 12 months (± 31 days). In addition, the participants have to fill in the HOOS, VAS, EQ-5D at 3 and 6 months. The questionnaires will be sent to the patient's home by post or e-mail. Participants will be able to return the questionnaire without making additional costs.

At the regular visit to the orthopaedic outpatient department at 8 weeks, radiographs of the pelvis will be taken according to the standard protocol (standing AP and lateral views) extra attention will be given for correct patient positioning for later migration analysis. At the regular visit to the orthopedic outpatient department at 12 months, balance and gait performance will again be tested using the TUG test and the two times 50 meter walk, both instrumented with inertial sensors. Also at 12 months standardized standing AP radiographs of the pelvis and axial radiographs of the treated hip will be made. One additional clinical radiological follow-up visit will be scheduled 24 months after surgery. At that moment, the participant will be asked to complete the HOOS, VAS and EQ-5D and the stem positioning will be assessed using standing AP pelvis and axial hip x-rays.

Table 1: Overview of the time schedule of the assessment of the study parameters

	1**	2**	3**	4**	5	6	8**	9***
Location	OC*	IC*	IC	OC	Q*	Q	OC	OC
Assessment	Pre-op	Operation	Day 1-3	8 weeks	3 months	6 months	12 months	24 months
Window				± 14 days	± 31 days	± 31 days	± 60 days	± 60 days
Parameter								
Demographic characteristics	X							
Clinical outcome								
HOOS	X			x	x	x	x	x
VAS	X		x	x	x	x	x	x
Hospital stay			x					
EQ-5D	X			x	x	x	x	x
Complications			x	x	x	x	x	x
Functional outcome								
HOOS	X			x	x	x	x	x
HHS	X			X			x	
Quality of balance and walking	X			x			x	
Surgical outcome								
Operation parameters		x						
Pelvic radiography	X		x	x			x	x

*OC: Outpatient Clinic; C: Inpatient Clinic; Q: Questionnaire sent to patient

** Standard patient visit

*** Extra outpatient visit

8.4 Withdrawal of individual subjects

Withdrawal is not to be expected, as a standard implant is being used and follow-up is close to routine follow-up of total hip arthroplasty following the protocol of the Noordwest Ziekenhuisgroep Alkmaar. Participants can stop participating in the study at any time for any reason if they wish to do so without any consequences. Patients who withdraw from the study will have the reason for their withdrawal recorded, if given, on the case report forms (CRF's). The postoperative assessments include standard evaluations according to the clinical protocol, so every attempt must be made to ensure that all the participants return for these controls. The researchers and/or the treating specialist involved can decide to withdraw a participant from the study for urgent medical reasons.

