8.4.1 Specific criteria for withdrawal

Not applicable

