8.6 Follow-up of subjects withdrawn from treatment

Participants who stop participating but do not withdraw their consent will be followed according to the standard clinical protocol currently used for patients with a total hip arthroplasty for recording of any adverse events. The patient shall not be asked to perform study related activities. It will be noted in the patient file if the patient no longer wishes to participate or if the patient has withdrawn informed consent.

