10. STATISTICAL ANALYSIS

10.1 Primary study parameter(s)

To answer our primary research question, subsidence at two years will be used. Secondary measurements include subsidence at 8 weeks and at 12 months. The EBRA-software needs at least 4 similar radiographs to correctly measure subsidence. The subsidence will be measured in mm with one decimal point behind the comma. In order to determine if there is a difference between the mean amount of subsidence (measured with the EBRA FCA) of the posterolateral and direct anterior approach group an independent t-test will be carried out and the 95% CI for the mean difference will be determined. Pearson's r will be used to calculate the effect size. The assumption of normality will be checked by visual inspection of the q-q plot and the box plot of the data within the groups. A Shapiro-Wilks test will also be performed on the data within the groups. Homogeneity of variance will be checked using the Levene's test.

The effect of time (e.g. at 1 day, 8 weeks, 12 months and 24 months postoperatively) on the amount of subsidence (measured with the EBRA FCA) will be examined with a one-way between subjects ANOVA. Eta^2 will also be calculated to determine the effect size. Tukey's HSD test will be used to identify where the specific differences occurred between the two groups. It is also used to calculate the 95% CI for each difference between the means.

The outcome parameters will be described in terms of means and standard deviations if the data are normally distributed. If the data are not normally distributed then they are described in terms of median, interquartile range and minimum and maximum values. Categorical study parameters are described as proportions.

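### A clinician's decision to withdraw a patient ends study follow-up and so loses the 24-month film that the primary outcome needs, possibly for reasons linked to fixation

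*Protocol*

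**What the plan says.** Protocol section 8.4 lets patients leave at any time and adds a second route out: "The researchers and/or the treating specialist involved can decide to withdraw a participant from the study for urgent medical reasons". The next entry, "8.4.1 Specific criteria for withdrawal", is marked as not applicable, so the ground is not defined further. On blinding, section 8.2 states: "Patient or surgeon will not be blinded for type of treatment".

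Section 8.6 describes what happens next. For participants who stop without revoking consent, the rule is that they "will be followed according to the standard clinical protocol currently used for patients with a total hip arthroplasty for recording of any adverse events". It continues: "The patient shall not be asked to perform study related activities". Section 8.5 rules out replacement.

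The 24-month assessment is additional to routine care. Section 5 says: "At 24 months we will schedule an additional clinical and radiological follow-up visit". Section 8.1.1 identifies the 24-month X-rays as the only ones outside standard treatment, and the assessment table in 8.3 marks that visit as extra. Section 10.1 fixes the primary analysis: "To answer our primary research question, subsidence at two years will be used". Sections 8.3 and 10.1 both require at least four films for EBRA.

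**The concern.** In a surgical trial with one intervention there is no study treatment left to stop after the operation. Withdrawal from the study can therefore only mean that data collection ends. Here someone other than the patient can end it, and the surgeon knows the approach used. No criteria are given, and the follow-up rule removes exactly the visit on which the primary comparison depends.

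The loss need not be random. Section 9.2.3 lists subsidence, migration and unintended fracture among the adverse device effects, so the protocol itself treats poor fixation as a medical event. Section 1 explains that early migration predicts later loosening. The patients for whom an urgent medical reason arises could include those the endpoint is meant to detect. If such losses differ between arms, the comparison of fixation is distorted, and an analysis plan cannot recover films that were never sought.

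**Working it through.** **Step 1: does withdrawal remove the primary outcome?**

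- Films showing the stem, from 8.1.1: postoperative, 8 weeks, 12 months, 24 months, so 4.
- Films required by EBRA, from 8.3 and 10.1: at least 4.
- Scheduled films left if the study-only 24-month film is not taken: 4 − 1 = 3, below the minimum.

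A patient withdrawn before 24 months thus has no two-year value, and the scheduled films do not meet the EBRA minimum. The sentence in 8.4 about making every attempt to bring participants back is tied to the standard evaluations, which do not include the 24-month visit.

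**Step 2: the plan's own sample size (section 4.4)**

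Inputs: difference 0.25 mm, SD 0.31 mm, two-sided 5%, power 80%.

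n per group = 2 × (1.96 + 0.842)² × 0.31² / 0.25² = 2 × 7.85 × 0.0961 / 0.0625 = 24.1, rounded up to 25. The noncentral t gives 25.1, with 79.8% power at 25. Allowance: 50 / (1 − 0.10) = 55.6, so 56. The plan's figures reproduce. The allowance covers 56 − 50 = 6 lost patients in number, but does nothing about which patients are lost.

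**Step 3: what selective loss could do**

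If k of n stems with mean m_lost go missing from an arm with mean m, the arm mean falls by k(m_lost − m)/(n − k).

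The protocol gives no withdrawal rate, so k is assumed to be 1 to 3 of 28 in one arm, with the largest values lost. Each scenario was simulated 20,000 times with SD 0.31 mm and a Student t-test on the remaining patients.

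No true difference (both means 0.46 mm), loss from DAA only:

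| Lost | Spurious DAA benefit, normal (mm) | Type I error, normal | Spurious DAA benefit, lognormal (mm) | Type I error, lognormal |
|---|---|---|---|---|
| 0 | 0.00 | 4.8% | 0.00 | 4.8% |
| 1 | 0.024 | 6.4% | 0.034 | 7.6% |
| 2 | 0.043 | 9.3% | 0.056 | 11.6% |
| 3 | 0.061 | 12.8% | 0.077 | 17.8% |

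True difference 0.25 mm, loss from PLA only, normal data: the estimate falls to 0.23, 0.21 and 0.19 mm for one, two and three stems lost. Power falls from 84% to 78%, 70% and 64%.

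Against the 0.25 mm target the shifts run from 0.02/0.25 = 8% to 0.08/0.25 = 32%. As a cross-check, one lost stem at the protocol's own 1.5 mm loosening threshold gives (1.5 − 0.46)/27 = 0.039 mm, or 0.039/0.25 = 15%.

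The bias comes from imbalance between arms. With a true difference of 0.25 mm and the three worst stems lost from each arm, the estimate stays at 0.25 mm in both distributions.

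**The case against.** The strongest reply is that the clause is narrow. It applies only to urgent reasons, section 8.4 does not expect withdrawals, and the body of 8.6 speaks of participants who stop, which most naturally describes patients who choose to. Not pressing study visits on them is ordinary practice. Films are read blind (8.1.1, 8.3), patients' reasons for withdrawal are recorded if given, and section 9.2.3 has component removals, subsidence and migration recorded as events, so failures would remain reportable.

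Part of this stands. The word urgent does limit the clause, and few patients may be affected. But the term is undefined, and the heading of 8.6 covers withdrawn subjects, with no other rule for patients withdrawn by a clinician. Blinded reading protects the measurement, not the decision about who gets a 24-month film. Event recording does not put a value into the t-test. Methods for missing data may well be in the SAP, but whether the film is sought after withdrawal is settled in the protocol.

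A reader might infer more than the documents support in three places:

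- **Sizing by revisions.** The registry table in section 1 gives 0.9% NANOS revisions at 3 years, or 56 × 0.009 = 0.5 expected. That does not measure the withdrawal rule: a stem revised before 24 months has no two-year value whatever 8.4 says, the table gives no cause of revision, and 3 years is not the endpoint time.
- **One grossly subsided stem.** A stem at 3 to 5 mm would have a much larger effect, but it would lie (3 − 0.46)/0.31 = 8 to (5 − 0.46)/0.31 = 15 SD above the planning mean, and nothing in the protocol supports assuming one.
- **Pregnancy.** Section 4.3 lists "Patient is pregnant or being pregnant during follow up intervals". This stands in an eligibility list, and 8.4.1 gives no withdrawal criteria, so it is weak evidence of a rule for removing patients after randomisation.

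**Conclusion.** The concern holds in a limited form. Followed as written, sections 8.4 and 8.6 lose the primary outcome of a clinician-withdrawn patient whose study stem is still in place, and that loss may be related to fixation. This is a stated rule, not a detail left to the SAP.

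How much it matters cannot be taken from the documents. The range of about 0.02 to 0.08 mm, with type I error of about 6 to 18%, assumes that one to three of the worst stems are lost from one arm only. Fewer losses, less selective losses or losses balanced between arms would do less harm. The text does not show that clinicians would use the clause selectively, only that nothing prevents it. Section 8.2 establishes that the surgeon is unblinded and is silent on the other researchers. The reading of 8.6 rests on its heading and on the absence of any other rule.

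**What to change.** Amend 8.4 and 8.6 as follows:

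1. Separate stopping individual study procedures from withdrawal of consent.
2. State that a decision by the researchers or treating specialist ends only the procedures that the patient cannot undergo.
3. State that the 24-month film is still sought from every consenting randomised patient with the study stem in place, and that the patient is analysed in the allocated arm.
4. Record each clinician-initiated withdrawal and its reason, and report these by arm.

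Handling of stems revised before 24 months can be left to the SAP. A pre-revision value could not simply be assumed available, because such a stem has at most three scheduled postoperative films.

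The cost is amendment wording, slight extra follow-up effort and films already planned for these patients. A few large values kept in the analysis may widen the confidence interval. The sample size of 56 and the operations are unaffected.
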